4 CLOSED REPORT TO THE DSMB

Closed reports are by treatment group, unless otherwise noted. Treatment groups will be labeled by letters. A sealed envelope to break the blind of the treatment groups will be provided with the report to the DSMB Chair.

4.1 **Baseline Characteristics**

Baseline characteristics provided in the open report will be summarized by treatment group in the closed report section. Summaries for continuous-valued outcomes by treatment group will include N and mean, SD or median, IQR. Summaries for categorical outcomes will include N and %.

P-values for comparisons of baseline characteristics between treatment groups will not be provided.

4.2 Data Completeness

Data completeness reports in the open report section (see 3.4) will be provided by treatment group in the closed section. The proportion of patients for which the day 28 form is available from among those who have completed the 28-day follow period will be compared between treatment groups using Fisher's exact's test.

4.3 Patient Profiles

A one page patient profile will be provided for each patient in the trial. This will provide a basic summary of their current status in the trial (i.e. treatment group, current study day, if they have been discharged, etc.). In addition, for each day, we will provide the CT value, vital signs, required chemistries (creatinine and potassium), days which infusions occurred and any SAEs.

4.4 Primary Outcome

The primary endpoint for this trial is 28-day mortality. All comparisons between treatment groups will follow the intent-to-treat principle, unless otherwise noted.

4.4.1 Primary analysis at study completion

Inference relating to the primary endpoint will quantify the probability that the 28-day mortality rate is lower (or higher) under ZMapp relative to oSOC using the Bayesian paradigm. A uniform(0,1) prior will be used for the 28-day mortality rate in both groups. The following summaries will be presented:

- 1. Basic summaries of 28-day survival (N and %) for each group, broken down into the following categories: dead, alive and still in follow-up period.
- Point estimate (all point estimates derived from Bayesian inference will use the posterior mean) and 95% credible interval (all credible intervals derived from Bayesian inference will use quantiles of the posterior distribution; i.e. 2.5th and 97.5th percentile) for the absolute difference in 28-day mortality rate between the two treatment arms.
- 3. Point estimate and 95% credible interval for the relative risk of 28-day mortality between the two treatment arms.
- 4. The posterior probability that arm A is superior to arm B, given the observed data.
- 5. Graphical displays of the updated posterior distribution for the absolute difference and relative risk, given the observed data.

The difference in 28-day mortality will be considered statistically significant if the posterior probability that the 28-day mortality rate in arm A is greater than the 28-day mortality rate in arm B is greater than 0.975 or vice versa.

Additional details about the computation of the posterior probabilities required for inference can be found in the following two documents: "Thumbnail sketch of Ebola

Treatment Trial Monitoring, with Examples" and "Monitoring a Trial of MCMs for Ebola Virus Disease."

4.4.1.1 INTERIM MONITORING AND ANALYSES

Interim analyses will first occur after the primary outcome is available for 12 subjects. Thereafter, interim analyses will be completed every 2 subjects until outcomes are available for 40 subjects, at which points interim analyses will occur after every 40 subjects. Ideally, the treatment groups would be balanced at the interim analyses (i.e. 6/group, 7/group, etc.) but, in practice, slight imbalances are expected at any point during the trial and this will have minimal impact on the operating characteristics of the proposed interim monitoring procedure.

The following summaries will be presented at all interim analyses:

- 1. Basic summaries of 28-day survival (N and %) for each group, broken down into the following categories: dead, alive and still in follow-up period.
- 2. Point estimate and 99.8% credible interval for the absolute difference in 28-day mortality rate between the two treatment arms.
- 3. Point estimate and 99.8% credible interval for the relative risk of 28-day mortality between the two treatment arms.
- 4. The posterior probability that arm A is superior to arm B, given the observed data.
- 5. Graphical displays of the updated posterior distribution for the absolute difference and relative risk, given the observed data.

The difference in 28-day mortality will be considered statistically significant at the interim analyses if the posterior probability that the 28-day mortality rate in arm A is greater than the 28- day mortality rate in arm B is greater than 0.998 or vice versa.

Conditional power will be included in DSMB reports after outcomes are available for 40 subjects. The conditional probability will be computed as the probability of a significant result at the end of the trial, as defined in Section 4.3.1, given the current data.

A detailed description of the interim monitoring for this trial, including the rationale and operating characteristics, can be found in a separate document entitled, "Monitoring a Trial of MCMs for Ebola Virus Disease."

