patient per arm, if necessary, up to 20. After that, monitoring would be after every 20 patients per arm until the target number of 100/arm is reached or the trial ends for other reasons. Any decision to curtail for other reasons will be made by a group blinded to trial results. The boundary we recommend is motivated from a Bayesian perspective. Bayesians formulate their prior opinion about the size of the treatment effect through a `prior' distribution, which is updated to a `posterior' distribution after observing data. We give details of the specification of the prior distribution and the construction of the boundary later. What are most important are the boundary itself and its statistical properties such as type I error rate (the probability of crossing the boundary inappropriately, i.e., when the 2 arms are equally effective) and power (the probability of crossing the boundary appropriately, i.e., when one arm is superior to the other).

Table 10 illustrates the design's flexibility by showing the boundaries assuming that factors beyond our control result in only 20 participants per arm by trial's end instead of the planned 100 per arm (stopping boundaries for 100 subjects per arm are included in Appendix B). For example, with 6 people evaluated in each arm, we declare superiority of one arm over the other only if all 6 die in one arm and none die in the other. On the other hand, with 10 people per arm, we cross the boundary if the numbers of deaths out of 10 in the 2 arms are as follows:

- 5. 7 or more and 0,
- 6. 8 or more and 1
- 7. 9 or more and 2
- 8. 10 and 3

Notice that the boundaries at the end of the trial are more lenient than interim boundaries: interim boundaries use a probability level of 99.9%, whereas the final boundary uses a level of 97.5%. This reinforces the need for a blinded group to make stopping recommendations for reasons other than safety or efficacy; otherwise, inflation of the type I error rate could result from lowering the boundary for the final analysis. Boundaries for a sample size of 100 per group will be generated following this same procedure and will be distributed to the DSMB.

Type I Error Rate

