Thoughtful specification of the prior distribution is crucial in Bayesian analysis. We want conclusions to depend primarily on data from the trial, not on prior opinion. This argues for a skeptical prior distribution that does not already assume that a treatment works. Let p denote the probability of survival in a given arm. Our prior distribution on p can be formulated by imagining having data on 2 people treated with a given agent, and observing that exactly 1 of the 2 survived. The probabilistic equivalent is to assume a beta prior distribution on p with parameters 1 and 1, equivalent to a uniform distribution on the interval (0,1). This is consistent with an overall survival probability of 0.50 for the current Ebola outbreak, but with wide variability reflecting substantial uncertainty about p. Moreover, a uniform distribution for p ensures very little influence of our prior opinion on conclusions. The observed data very quickly dominate in decision-making. For instance, if 20 people are given the treatment and 12 of them survive, the posterior distribution for the survival probability is beta with parameters 13 and 9. In other words, combining our prior opinion with the observed data equates to observing 13+9=22 people, 13 of whom survived. Our prior opinion constitutes only 2 of the 22

people, and therefore has very little effect on the conclusions. Also, we use the same prior distribution in different arms. That way, our prior opinion does not favor any treatment over oSOC. If p_A and p_B denote the survival probabilities in arms A and B, respectively, we use independent beta posterior distributions in the 2 arms to calculate the probability that $p_A < p_B$, namely that the survival probability in arm B exceeds that in arm A. At any interim analysis preceding the final analysis, we declare arm B superior if this probability exceeds 99.9%. At the final analysis, we declare superiority of arm B if this probability exceeds 97.5%.

Analyses

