 - B. The second alpha level is adjusted using the Haybittle-Peto monitoring procedure:

 α =0.025-(0.001)k, where k is the number of interim looks at the data.

A confidence interval will be computed for the absolute risk difference using Barnard test methodology and confidence level $1-2\alpha$. This will be done for each of the two alpha levels specified above.

- The same approach specified above for Barnard's test, including the two separate alpha levels, will also be performed for Fisher's exact test. A confidence interval for the odds ratio will be computed using the non-central hypergeometric distribution.
- An analysis of time to death will be performed using a log-rank test. In addition, a stratified log-rank test will be performed with 4 strata defined by location and cycle threshold. (See description of stratification variables below). This will be done for each of the two alpha levels specified above. Tests of treatment by subgroup interaction will be performed.

Stratification and subgroup analyses

- Additional analyses will be performed within two strata defined by cycle threshold: ≤22 versus >22 for all subjects. To assess whether there is a treatment by cycle threshold interaction, we will compute the posterior probability that the treatment effect (absolute or relative) differs by cycle threshold.
- Analysis combining the United States, Liberia, and Sierra Leone as one location stratum, while Guinea constitutes the other location stratum. (The standard of care in Guinea typically included favipiravir, which was not the case in the other countries). Note that the protocol initially specified stratified randomization for the USA. However, only one patient in the USA was randomized, which is why the location strata have been changed to USA/Liberia/Sierra Leone vs Guinea. To assess whether there is a treatment by location interaction, we will compute the posterior probability that the treatment effect (absolute or relative) differs by location. An additional sensitivity analysis will exclude the lone patient treated in the United States. The treatment effect within the United States versus West Africa could make interpretation of results more difficult. For example, if the patient was assigned to oSOC and survived, that may simply reflect better oSOC in the United States.

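### The Data Analysis Plan declares interim significance at a posterior probability of 0.998 in either direction, where the protocol and its published boundaries use 0.999

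*Combined protocol and SAP*

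**What the plan says.** **Protocol, section 22.** Under Interim Monitoring, "interim boundaries use a probability level of 99.9%, whereas the final boundary uses a level of 97.5" percent. Technical Details of Boundary Construction applies this to one direction: "At any interim analysis preceding the final analysis, we declare arm B superior if this probability exceeds 99.9" percent. For the end of the trial: "At the final analysis, we declare superiority of arm B if this probability exceeds 97.5" percent. Tables 10 to 12 give the resulting boundaries, error rates, power and average sample sizes.

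**DAP, section 4.4.1.1.** This section specifies what the DSMB sees at each interim look. It asks for "Point estimate and 99.8% credible interval for the absolute difference in 28-day mortality rate between the two treatment arms", and the same for the relative risk. It then calls the difference significant if the posterior probability that the 28-day mortality rate in arm A exceeds the "mortality rate in arm B is greater than 0.998 or vice versa".

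**DAP, section 4.4.1.** "A uniform(0,1) prior will be used for the 28-day mortality rate in both groups", and "all credible intervals derived from Bayesian inference will use quantiles of the posterior distribution". At study completion this section pairs a 95% interval with a threshold of 0.975 in either direction.

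**Final Data Analysis Plan (January 2016), section 3.8.** The adjusted alpha for the supportive frequentist tests is "0.025-(0.001)k, where k is the number of interim looks at the data".

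**The concern.** A threshold of 0.998 with its mirror image leaves 0.002 in each direction, twice the 0.001 that the protocol allows. The likely origin is that the two-sided interval level, 99.8%, was copied into a one-directional rule. The documents do not say so, and none of the text provided justifies 0.998.

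Three other places point to 0.999: the protocol text, the 99.8% equal-tailed intervals in the same DAP section, and the 0.001 deducted per look in the Final DAP.

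At stake is the criterion by which an experimental arm is judged superior on mortality and, under the protocol's design, may become part of the new standard of care. With two levels in force, the same data can be significant under the DAP and short of the boundary under the protocol. One DSMB report could also call a difference significant beside an interval that includes zero.

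**Working it through.** **Inputs.**
- Uniform(0,1) prior on mortality in each arm (protocol section 22; DAP 4.4.1).
- Looks at 6, 7, …, 20, 40, 60, 80 and 100 per arm (protocol section 22). The DAP schedule of 12 subjects, then every 2 up to 40, then every 40, is the same when arms are balanced.
- Final threshold 0.975 per direction in both documents.
- Interim threshold 0.999 (protocol) or 0.998 (DAP).

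**Method.** After x deaths among n patients, the posterior for an arm's mortality is Beta(x+1, n−x+1). The posterior probability that one arm's mortality exceeds the other's is computed from the two independent betas. A forward recursion over the pair of death counts accumulates the exact probability of crossing at each look, in either direction.

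**Step 1: reproduce the protocol at 0.999.**
- All 87 interim boundary cells in Table 10 (6 to 19 per arm) match. The 20-per-arm column matches at the final level of 0.975.
- Type I error at mortality 0.5 in both arms, 100 per arm: 0.0637 (Table 11: 0.063, simulated).
- Power at 100 per arm: 0.879 for 0.2 versus 0.4 (Table 11: 0.88), and 0.834 for 0.3 versus 0.5 (Table 11: 0.83).
- Average size for 0.3 versus 0.5: 83.9 per arm (Table 12: 84).

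The published properties therefore describe the 0.999 rule.

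**Step 2: repeat at 0.998, with 100 per arm and equal mortality.**

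| Mortality in both arms | False interim crossing, 0.999 | False interim crossing, 0.998 | Ratio | Overall type I, 0.999 | Overall type I, 0.998 |
|---|---|---|---|---|---|
| 0.1 | 0.0027 | 0.0064 | 2.4 | 0.0475 | 0.0490 |
| 0.2 | 0.0063 | 0.0141 | 2.2 | 0.0512 | 0.0560 |
| 0.3 | 0.0094 | 0.0193 | 2.05 | 0.0547 | 0.0613 |
| 0.4 | 0.0115 | 0.0224 | 1.95 | 0.0583 | 0.0657 |
| 0.5 | 0.0127 | 0.0236 | 1.86 | 0.0637 | 0.0713 |

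Power hardly moves: 0.881 against 0.879 for 0.2 versus 0.4, and 0.837 against 0.834 for 0.3 versus 0.5. Average size for 0.3 versus 0.5 falls from 83.9 to 78.3 per arm. The boundary changes in 11 of the 14 interim columns of Table 10, all except 6, 7 and 13 per arm.

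**Step 3: one case by hand.** Take 10 per arm with 6 versus 0 deaths. The posteriors are Beta(7,5) and Beta(1,11).
- With no deaths in the second arm, the probability that its mortality exceeds the first arm's mortality p is E[(1−p)^11], where 1−p follows Beta(5,7).
- This equals (15! × 11!)/(4! × 22!) = 0.00193, so the posterior probability is 1 − 0.00193 = 0.9981.
- That exceeds 0.998 but not 0.999. Table 10 requires 7 versus 0 in this column, where the same formula gives (14! × 11!)/(3! × 22!) = 0.00052 and a posterior probability of 0.9995.
- The equal-tailed 99.8% interval for the difference at 6 versus 0 runs from about −0.04 to 0.885, so it includes zero.

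By symmetry, 10 versus 4 deaths at 10 per arm has the same posterior probability and is also newly significant.

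**Step 4: interval and threshold.** A 99.8% equal-tailed interval leaves (1 − 0.998)/2 = 0.001 in each tail, which pairs with 0.999 per direction. A 95% interval leaves 0.025 per tail and pairs with 0.975, as the DAP has it at study completion. The interim pair breaks this pattern.

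**Step 5: the Final DAP deduction.** It records 7 DSMB reviews. If all count as looks, the adjusted alpha is 0.025 − 7 × 0.001 = 0.018. A charge of 0.002 per look would give 0.025 − 7 × 0.002 = 0.011. The second figure is approximate, since it equates a posterior threshold with a frequentist charge.

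**The case against.** The other side accepts the discrepancy and the figures, and disputes how much they matter.

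- **Only the interim part doubles.** This is correct. Most of the error is spent at the final 0.975 look, which is common to both documents, so overall type I error at mortality 0.5 rises by 0.0713 − 0.0637, or about 0.8 percentage points. The protocol already accepts about 6% and does not aim at strict control.
- **The boundaries are advisory.** Also correct. The DAP calls a result significant; it does not order a stop, and the DSMB weighs several factors. The protocol also says that boundaries built at 99.9% will be distributed to the DSMB. This softens the consequence but leaves the board with two criteria.
- **The trial did not run to 100 per arm.** The Final DAP records 72 patients at planned closure. Assuming 36 per arm, looks at every size from 6 to 20 and a final look at 36, overall error is 4.9% against 5.5% (mortality 0.5) and 5.2% against 5.6% (0.3). The actual look times are not given, so this is illustrative, but the realised effect is probably about half a point.
- **No harm is recorded, and the Final DAP has no 0.998 rule.** All seven reviews recommended continuing, and the primary criterion is unaffected. However, the Final DAP restates no interim threshold, so the DAP sentence remains uncorrected.
- **Other monitoring documents exist.** The DAP refers to a separate monitoring document that is not available here. It may use 0.999. That is a reason to ask which level was used, and does not resolve the conflict.

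These points limit the practical consequence. None of them supports 0.998.

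**Conclusion.** The concern holds. The DAP's interim criterion is looser than the protocol's, disagrees with the DAP's own 99.8% intervals, and is not the rule whose properties the protocol publishes. With the planned looks, balanced arms and uniform priors, it multiplies the probability of a false interim crossing by 1.9 to 2.4 over mortality 0.1 to 0.5. It raises the maximum overall type I error from 6.4% to 7.1% and alters 11 of the 14 interim boundary columns of Table 10. The protocol's tables cannot be used to describe it.

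The documents do not show which level was applied in the DSMB reports, and no interim efficacy stop is recorded. The correction is still needed, because the sentence defines when a mortality difference is declared.

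**What to change.** In DAP section 4.4.1.1, replace 0.998 with 0.999 in each direction. Keep the 99.8% credible intervals, which then agree with the threshold and with the protocol.

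Ask the unblinded statisticians to confirm, in a note to the DSMB file, which level each interim report used. If it was 0.999 throughout, nothing more is needed, and the cost is one number and a note.

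If any look used 0.998, restate the boundaries, type I error and average sample sizes of Tables 10 to 12 for the rule applied. In that case also revisit the per-look deduction in section 3.8 of the Final DAP, where 0.002 for each such look is a reasonable approximation. That would mean rerunning the operating characteristics and the adjusted-alpha supportive tests and intervals. The primary criterion of 0.975 does not change, and no additional patients are needed in either case.

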4.4.1.2 PARTIALLY OBSERVED OBSERVATIONS

The analysis described above only utilizes subjects for which the primary endpoint has been fully observed (i.e. death or 28-day survival). At the interim analyses, there will be subjects that have been enrolled and randomized but have yet to complete the 28-day follow-up period. In this case, we will complete a sensitivity analysis to determine how the results of the analysis presented in Section 4.3.1.1 would change depending on the outcomes for these subjects. Specifically, we will present the summaries described in Section 4.3.1.1 assuming that all remaining subjects in group A will survive, while all subjects in group B will die and assuming that all remaining subjects in group B will survive, while all subjects in group A. This will provide a "worst-case-scenario" for how

much the results of our primary analysis could change based on the outcomes of the partially observed subjects.

4.4.1.3 EARLY TERMINATION FOR EXTERNAL REASONS

There are several scenarios where the trial may terminate early for external reasons (end of the epidemic, inadequate drug supply, etc.). This situation is discussed in more detail in guidance document provided to the DSMB. In the event that the trial is terminated for external reasons, we will summarize the difference in 28-day mortality rate by group as described in Section 4.3.1 and the difference between groups will be declared statistically significant if the posterior probability that the 28-day mortality rate in arm A is greater than the 28-day mortality rate in arm B is greater than 0.975 or vice versa.

4.4.2 Additional analyses

4.4.2.1 STRATIFIED ANALYSIS

In addition to the above grouped summaries, we will also complete a stratified analysis by the location of treatment (West Africa vs. U.S.) and CT value (> 22 vs. \leq 22). Stratified analyses will be completed separately for the two stratification factors and will be completed once data are available for the two stratum. Analyses will be completed assuming the Bayesian paradigm with uniform(1,1) prior distributions for the 28-day mortality rate in each stratum. The following summaries of the stratified analyses will be reported:

- 1. Basic summaries of 28-day survival (N and %) for each group within a stratum, broken down into the following categories: dead, alive and still in follow-up period.
- 2. Point estimate and 99.8% credible interval for the relative risk of 28-day mortality between the two treatment arms for each stratum.
- 3. The posterior probability that the relative risk in stratum 1 is greater than the relative risk in stratum 2. The relative risks will be considered significantly different if the posterior probability is greater than 0.975 or less than 0.025.

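### The DSMB analysis plan calls stratum relative risks significantly different at the final-analysis level, with no stricter level for interim reports

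*Combined protocol and SAP*

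**What the plan says.** DAP section 4.4.2.1 (Stratified Analysis) sits within section 4, the closed report to the DSMB. The DAP's table of reports says closed reports are prepared before each DSMB meeting. The stratified analysis covers location and CT value (above 22 versus 22 or below), taken one at a time, and "will be completed once data are available for the two stratum". For each stratum it gives "Point estimate and 99.8% credible interval for the relative risk of 28-day mortality between the two treatment arms for each stratum". For the comparison between strata it gives the posterior probability that one relative risk exceeds the other, with the rule "The relative risks will be considered significantly different if the posterior probability is greater than 0.975 or less than 0.025". It does not separate interim from final reports.

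The overall comparison is handled differently:

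- **Final analysis, DAP 4.4.1:** significance when the posterior probability that mortality in arm A exceeds the "mortality rate in arm B is greater than 0.975 or vice versa".
- **Interim, DAP 4.4.1.1:** the same statement with "rate in arm B is greater than 0.998 or vice versa".
- **Interim, protocol section 22 (Technical Details of Boundary Construction):** "At any interim analysis preceding the final analysis, we declare arm B superior if this probability exceeds 99.9" per cent.
- **Look schedule, DAP 4.4.1.1:** the first look is at 12 outcomes, then "interim analyses will be completed every 2 subjects until outcomes are available for 40 subjects", then after every 40.

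**The concern.** The documents accept that repeated looks call for stronger evidence before the end. Protocol section 22 contrasts a 99.9% interim level with a 97.5% final level, and warns that using the lenient level at the wrong time could inflate the type I error rate. The stratum comparison rests on four small cells rather than two arms, yet it gets no such protection. At one and the same interim look, the overall effect needs at least 0.998 while a CT interaction is labelled significant at 0.975.

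At stake is what the DSMB reads. CT became a stratification factor because early data linked it to outcome (Summary of Amendments, amendment B). A report that the treatment effect differs significantly by CT would therefore carry weight with a board that may recommend modifying the study (protocol 26.9.3).

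**Working it through.** **Inputs from the documents.** Level 0.975/0.025 (DAP 4.4.2.1). Interim level 0.998 (DAP 4.4.1.1) or 0.999 (protocol section 22). Maximum 200 patients, 1:1 (DAP section 1). Looks at 12, 14, ..., 40, which is (40 - 12)/2 + 1 = 15, then 80, 120, 160 and 200, which is 4: 19 in all, the last being final. The January 20, 2016 final plan reports 7 DSMB reviews of interim data and 72 patients randomized (section 2), and one U.S. patient (section 3.8). The stratum prior is printed as "uniform(1,1) prior distributions for the 28-day mortality rate in each stratum". It is read here as beta(1,1), matching the uniform(0,1) prior of DAP 4.4.1.

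**Assumptions, not in the documents.** True relative risk 1 in both strata. CT split 50/50 or 40/60. Stratum mortality 0.2 to 0.7. For a lopsided factor, 5% or 10% of patients in the small stratum. Approximately even spacing for the 7 reviews. At least one patient in each of the four arm-by-stratum cells before a comparison is made.

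**Step 1: the plan's own figures.** The documents state no error rate for the stratum comparison, so the overall rule was reproduced first (99.9% interim, 97.5% final, 19 looks, 100 per arm; 60,000 simulated trials per scenario).

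| Quantity | Protocol Table 11 | Recomputed |
|---|---|---|
| Type I error, mortality 0.1 / 0.2 / 0.3 / 0.4 / 0.5 | 0.048 / 0.053 / 0.055 / 0.057 / 0.063 | 0.048 / 0.051 / 0.056 / 0.059 / 0.062 |
| Power, 0.2 v 0.4 | 0.88 | 0.877 |
| Power, 0.3 v 0.5 | 0.83 | 0.833 |

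**Step 2: the stratum rule.** In arm j and stratum s, with x deaths among n patients, the posterior for mortality p_js is beta(x + 1, n - x + 1). Put RR_s = p_1s / p_0s. The rule flags when P(RR_1 > RR_2) is above 0.975 or below 0.025. The probability was computed numerically from the four independent beta posteriors and checked against Monte Carlo draws. Each scenario used 12,000 to 20,000 null trials. At 12,000 trials the simulation standard error at a rate of 0.16 is sqrt(0.16 x 0.84 / 12,000) = 0.003.

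| Mortality in strata 1, 2; share in stratum 1 | Final look only (200) | Any of 19 looks | Ratio | Any of 7 looks to 72 patients |
|---|---|---|---|---|
| 0.5, 0.5; 50% | 0.047 | 0.197 | 4.2 | 0.125 |
| 0.3, 0.3; 50% | 0.047 | 0.176 | 3.8 | 0.116 |
| 0.2, 0.2; 50% | 0.047 | 0.154 | 3.3 | 0.092 |
| 0.6, 0.2; 50% | 0.052 | 0.160 | 3.1 | 0.097 |
| 0.6, 0.2; 40% | 0.046 | 0.158 | 3.4 | 0.104 |
| 0.7, 0.3; 50% | 0.045 | 0.172 | 3.8 | 0.111 |
| Lopsided: 0.4, 0.4; 5% | 0.031 | 0.057 | 1.8 | 0.013 |
| Lopsided: 0.4, 0.2; 90% | 0.029 | 0.067 | 2.3 | 0.027 |

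A repeat run of the first row gave 0.203 over 19 looks and 0.126 over 7. In the six CT-like rows, a single look at 72 patients flags 0.041-0.047, so the 7-look ratio in this table is 2.3-2.7 (up to 2.9 in the repeat run). Seven equally spaced looks to 200 patients give 0.134-0.155. Stopping on the overall boundary barely matters: in the repeat run, 0.203 becomes 0.201.

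**Step 3: an interim level for the flag.** With 0.975/0.025 kept for the final look only, over 19 looks:

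| Mortality (50/50 split) | As written | 0.998 at interims | 0.999 at interims |
|---|---|---|---|
| 0.5, 0.5 | 0.203 | 0.060 | 0.055 |
| 0.3, 0.3 | 0.173 | 0.055 | 0.051 |
| 0.6, 0.2 | 0.157 | 0.051 | 0.048 |

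**The case against.** The case on the other side has several parts, and much of it stands.

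- **Interim use is inferred.** A reader might conclude that the flag appears in every closed report. The text does not say so. It starts the analysis once both strata have data, and the five summaries that DAP 4.4.1.1 requires at all interim analyses do not include it. Its place in the closed report, its trigger, its category for patients still in follow-up and its 99.8% interval make interim use a fair reading, but not a stated one.
- **The inflation is not one number.** A reader might say that the error rate triples. That fits a balanced CT factor on the planned schedule (3.1 to 4.2 times). It does not fit 7 reviews and 72 patients (2.3 to 2.9 times), nor a lopsided factor (about 2 times, from a base near 3%). With one U.S. patient, at least one U.S. arm is empty, so no meaningful U.S. versus West Africa comparison existed.
- **The 99.8% interval does not contradict the rule.** A reader might see a mismatch between the two. The interval is for the treatment effect within a stratum and the rule compares strata. The interval shows only that interim reports were in mind.
- **No decision hangs on the flag.** A reader might infer that a false flag would restrict enrolment or alter the trial's conclusion. Nothing ties it to stopping. Even the overall boundaries are advisory, and protocol section 22 has the DSMB weigh several factors. The board also sees the stratum counts and the posterior probability. Section 3.8 of the January 2016 plan computes the CT and location interaction probabilities without a threshold.

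None of this supplies an interim level where DAP 4.4.2.1 gives none.

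**Conclusion.** The concern holds in a limited form. DAP 4.4.2.1 attaches the final-analysis level to an analysis evidently meant for interim DSMB reports, while the overall comparison is held to 0.998 or 99.9% at those looks. With no true interaction and CT strata of similar size, the chance of at least one false flag is about 15-20% over the 19 planned looks, against about 5% at a single final look. It is about 9-13% for 7 looks to 72 patients. These figures rest on assumed stratum shares, mortality and, for the 7 reviews, timing. For a lopsided factor the 19-look figure is about 6-7%.

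The effect is confined to how the DSMB is told to read a subgroup result at interims. The documents do not support a claim that it compromises the final inference. The protocol's own 97.5% statement about strata, under Analyses in section 22, does not mention repeated looks and is not the subject of this point.

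**What to change.** In DAP 4.4.2.1, restrict the significance statement at 0.975/0.025 to the final analysis. For interim reports, state that the same interim level applies as for the overall comparison. That level must be settled first: DAP 4.4.1.1 uses 0.998 and the protocol 99.9%, while the DAP's own 99.8% interval leaves (100 - 99.8)/2 = 0.1% in each tail, which corresponds to 0.999/0.001. Tightening only the subgroup rule would hold it to a stricter interim level than the DAP's primary comparison.

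Either level removes most of the inflation: 4.8-5.5% cumulative with 0.999/0.001, and 5.1-6.0% with 0.998/0.002. Keep reporting the posterior probability at every look, as the section already provides. In the same edit, correct the stratum prior to beta(1,1), that is, uniform(0,1).

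The cost is a sentence in 4.4.2.1 and the reconciliation of one number. The downside is that a real interaction is formally flagged later, although its probability remains visible to the DSMB throughout.
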